surface through visual inspections (Merletti et al. 2004; Barbero et al. 2011; Beretta Piccoli et al. 2014; Boccia and Rainoldi 2014; Guzmán-Venegas et al. 2014) or automatic algorithms such as bi-dimensional cross correlation (Cescon 2006; Beck et al. 2012; Cescon et al. 2014; Ullah et al. 2014), template matching (Mesin et al. 2009; Jahanmiri-Nezhad et al. 2015) or optical flow (Östlund et al. 2007). Those surface IZ mapping techniques have also been used to localize IZs over the skin surface to improve the BTX injection outcome, but the application of those surface localization method is limited by the lack of depth information of the IZs. Clinically, the motor point (MP) is used as the injection site of BTX since it is homologous to the IZ. However, a significant difference between the MP and IZ locations has been observed (Guzmán-Venegas et al. 2014). The bipolar high-density surface EMG mapping has also been used to localize IZs over the skin surface to improve the BTX injection outcome (Lapatki et al. 2011), but the application of this surface localization method is limited by the lack of the depth information of the IZs, particularly due to peripheral adaptive changes including atrophy and fat tissue deposit (Gracies 2005). 3D IZ location technique is therefore needed in order to improve clinical outcomes with minimum treatment dose and thus to minimize side effects.

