The surface position of the IZ of a particular MU can be identified from the bipolar map of the decomposed high-density MUAPs by checking the phases of the propagating signals. A cylinder with the diameter of 20 mm (Buchthal and Sten-Knudsen 1959; Merletti et al. 1999) is defined right underneath the identified surface IZ location and axially pointed to the normal direction of the skin surface, and the cylinder will create a cylindrical shaped sub-space in the target muscle space. A high weighting factor

(0.9) is applied to the cylindrical sub-space and a low weighting factor (0.1) is applied to the rest 3D muscle space, and the source covariance matrix R in Equation (2) is then calculated accordingly.

Evaluation of the 3DIZI in computer simulations

A series of computer simulations were conducted based on the FE model of the upper arm in Fig. 1 to evaluate and optimize the performance of the 3DIZI approach in localizing IZs in the 3D space of the biceps. One extended activation zone in an ellipsoidal shape with semi-axes length of 5 and 4 mm in parallel and normal to the muscle fiber directions were assumed in the biceps, with different depths (10, 15 and 20 mm depths from the skin surface) (Merletti et al. 1999; Merletti et al. 2008). At each depth, one activation zone was assumed at 6 locations in the biceps along the muscle fiber direction, or one pair of activation zones were assumed at 3 different locations which are symmetrical to the mid-axial plane the biceps. The electrical potentials at 128 EMG electrode locations were calculated based on the FE model as the simulated surface EMG measurements after adding Gaussian white noises at different noise levels (SNRs = ∞ , 30, 25, 20) (Phinyomark et al. 2012).

The localization error (LE) was employed to evaluate the accuracy of the 3DIZI results. The LE is defined as the spatial distance between the center of the assumed target activation zone and that of the reconstructed muscle activation zone. For the cases with two activation zones, the LE was calculated by averaging the two individual LEs. Fig. 4 presents the mean and standard deviation of LEs achieved at different noise levels and source depths. The noise and source depth does affect the accuracy of the 3DIZI results, but the all mean LEs are less than 5 mm for all the cases, which demonstrates the high performance of the 3DIZI.

[figure not shown]
[figure not shown]

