The purpose is to evaluate the performance of the 3DIZI approach in localizing IZs in the 3D space of the spastic muscles with simultaneous high-density surface EMG and intramuscular EMG recordings.

Eight patients with spastic biceps will be recruited to participate in this validation study in TIRR. The same protocol will be used as described in our preliminary study (Liu et al. 2015).

Simultaneous surface EMG and intramuscular EMG recordings: Simultaneous surface EMG and intramuscular EMG measurements will be acquired from the spastic biceps of the patients with a 136-channel Refa (TMSi, Enschede, The Netherlands). Patients will be seated comfortably on a height-adjustable chair. The arm to be tested will be secured firmly on a customized apparatus with the elbow joint at approximately 90 of flexion and the shoulder at approximately 45 of abduction and 30 of flexion. The 128-channel unipolar surface EMG signals will be recorded with 2 flexible 2-dimensional 64-channel (in 8x8 formation, individual recording probe 4.5 mm in diameter, center-to-center probe distance 8.5

mm) surface electrode array (TMSi, Enschede, The Netherlands). The skin of the tested muscle will be carefully prepared, and the electrode array was attached to the biceps muscles with a double adhesive sticker and further secured with medical tapes. A coating fine wire electrode (VIASYS Healthcare, Madison, WI) will be inserted into the mid-axial section of the biceps to record bipolar intramuscular EMG signals. Ultrasound scan (M Turbo, SonoSite, Bothell, WA) will be performed on the biceps to identify the location of the inserted wire electrode. Patients will be asked to contract their impaired biceps to perform maximum voluntary contraction (MVC) of elbow flexion against the vertical plates 3 times. Each trial will last for 10 sec. A sampling rate of 2 KHz will be used for simultaneous surface and intramuscular EMG recordings during muscle contraction.

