Validation: 1) The recorded 128-channel surface EMG signals will be first decomposed into their constituent MUAP trains using the KmCKC approach (Ning et al. 2015); 2) Correlations between each MUAP trains and the intramuscular EMG signals will be calculated to identify the MUs which were simultaneously recorded by both the surface EMG and wire EMG electrodes; 3) the muscle activities of the MUs, which were simultaneously recorded by both surface EMG and wire EMG electrodes, will be reconstructed in the 3D space of the biceps from their MUAPs respectively using the 3DIZI approach; 4) the localization error (LE), defined as the distance between the center of the reconstructed muscle activation zone or IZs and the location of the inserted wire electrode identified in ultrasound images, will be calculated. The mean value and standard deviation of LEs achieved from each patient will be calculated to evaluate the accuracy of the 3DIZI results.

Pitfalls: Attempts will be made to insert the wire electrode into IZs in the mid-axial section of the biceps so that muscle activities in IZs can be recorded. However, it is possible that the wire electrode will not be inserted into any IZ of the specific biceps and no muscle activities in IZs can be measured. In this case, the propagating muscle activities measured by the wire electrode, as demonstrated in Fig. 5(a2) - (c2) will be used to evaluate the proposed 3DIZI approach. For patients who cannot contract their spastic biceps efficiently, electrical stimulation will be delivered to the musculocutaneous nerve using an electrical stimulator (D7SA, Digitimer Ltd, Hertfordshire, England) to generate a maximum response. Techniques for removal of stimulation artifacts have been recently developed by our group (Li et al. 2014).

Experiment 2: Evaluation of the feasibility of utilizing the 3DIZI to optimize the BTX injection

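### Experiment 1 plans no comparator localization method and does not separate depth error from lateral error, so a small localization error cannot by itself show that 3D depth imaging adds information

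*Combined protocol and SAP*

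**What the plan says.** Section 3 (Background) gives the reason for a 3D method. Surface mapping of innervation zones (IZs) already exists, but "the application of those surface localization method is limited by the lack of depth information of the IZs". Depth is the claimed advance.

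Section 3 (3DIZI Inverse Solution) describes how the surface IZ enters the method. "A cylinder with the diameter of 20 mm" is placed under the surface IZ of each motor unit, with weight 0.9 inside it and 0.1 in the rest of the muscle.

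Section 3 (Evaluation of the 3DIZI in computer simulations) tests sources at 10, 15 and 20 mm depth and reports LE as a single 3D distance between zone centres: "but the all mean LEs are less than 5 mm for all the cases, which demonstrates the high performance of the 3DIZI".

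Section 4 (Experiment 1) recruits eight patients and inserts one fine wire per patient into the mid-axial section of the biceps. Motor units are matched to the wire by correlation. LE is the distance from the reconstructed zone centre to "the location of the inserted wire electrode identified in ultrasound images, will be calculated". If the wire misses every IZ, propagating activity is used instead. The analysis is "The mean value and standard deviation of LEs achieved from each patient will be calculated to evaluate the accuracy of the 3DIZI results". The plan gives no comparator method, LE limit, confidence interval or separate depth error.

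**The concern.** LE is one number that mixes two components. The lateral component owes much to the surface IZ, which is available without 3DIZI. The depth component is what the inverse solution has to supply. If only their combination is reported, a working depth method and surface mapping plus a default depth may give similar results.

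The single wire per patient makes this harder to see. All matched motor units in a patient are scored against the same point, so the per-patient mean and SD describe scatter around one depth. They do not show whether estimated depth follows true depth. Across the study there are at most eight reference depths, and the plan does not report their spread.

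Experiment 2 cannot fill the gap. Its standard arm uses ultrasound to confirm that the needle is in the muscle, without IZ information. A benefit in the guided arm could come from surface IZ position alone. What is at stake is whether the project can conclude that the third dimension matters.

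**Working it through.** **Inputs from the document.** Simulated depths 10, 15 and 20 mm; all simulated mean LEs below 5 mm; cylinder diameter 20 mm with weights 0.9 and 0.1; electrode pitch 8.5 mm; eight patients, one wire each.

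**Assumptions, because the document gives no figure.** The lateral error of the surface IZ, and the depth distribution of IZs in spastic biceps.

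**Step 1: the plan's own figure.** The bound of 5 mm cannot be reproduced. It needs the finite element model and a figure that is not shown. It is used here only as an upper bound.

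**Step 2: what one LE reveals.** LE² = lateral² + depth². An LE of 5 mm is compatible with any depth error from 0 to 5 mm.

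**Step 3: a guess with no imaging.** Take the surface position, fix the depth at 15 mm, and let e be the lateral offset. At true depth d, error = √((d − 15)² + e²).

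| e (mm) | d = 10 | d = 15 | d = 20 | Pooled mean |
|---|---|---|---|---|
| 0 | 5.0 | 0.0 | 5.0 | 3.3 |
| 2 | 5.4 | 2.0 | 5.4 | 4.3 |
| 3 | 5.8 | 3.0 | 5.8 | 4.9 |
| 5 | 7.1 | 5.0 | 7.1 | 6.4 |

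The pooled mean is (2√(25 + e²) + e)/3 and reaches 5 mm at e of about 3.2 mm. With lateral error uniform within half a pitch on both axes (8.5/2 = 4.25 mm either way), simulation with 2,000,000 draws gives a pooled mean of 5.1 mm. Within a full pitch it gives 7.7 mm.

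**Step 4: sensitivity to the guess.** With e = 0, a guess of 12.5 mm gives (2.5 + 2.5 + 7.5)/3 = 4.2 mm. A guess of 10 mm gives (0 + 5 + 10)/3 = 5.0 mm. By symmetry 17.5 and 20 mm give the same, so 3.3 mm is the best case.

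**Step 5: sensitivity to the depth distribution.** For depths uniform over a range, a midpoint guess has mean depth error of range/4. That is 10/4 = 2.5 mm for 10–20 mm and 20/4 = 5.0 mm for 5–25 mm (both ranges assumed).

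**Step 6: precision of a paired comparison.** With eight patients the 95% t interval has half-width 2.365 × SD/√8 = 0.84 SD. If the SD of the patient-level differences were 1, 2 or 3 mm (assumed), the half-width would be 0.8, 1.7 or 2.5 mm.

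**The case against.** The strongest reply concerns the comparison with 5 mm. The plan says "the all mean LEs are less than 5 mm for all the cases", and the caption of Fig. 4 shows results by noise level and depth. The fixed guess has an error of at least 5.0 mm at 10 and at 20 mm even with perfect lateral position. It stays below 5 mm only when pooled over depths. A reader might infer from the 3.3 mm that a guess matches or beats 3DIZI in the simulations. The document does not support that: meeting the bound at 10 and 20 mm does beat the guess. This objection stands in full.

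Four more points stand in part.

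- Experiment 1 has a reference standard, the wire seen on ultrasound. What is missing is a comparator.
- The three depths are simulation settings. Nothing in the document says that IZ depth in spastic biceps is confined to 10–20 mm, and Section 3 names atrophy and fat deposits as reasons why depth matters.
- The surface IZ is a soft constraint. The zone centre can move within the cylinder and is estimated on a 2 mm grid, so lateral position is not simply copied.
- Absolute error has meaning of its own. Section 3 cites a 46% loss of toxin effect per 1 cm from the IZ, and Experiment 1 is an exploratory evaluation with no stated pass mark.

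These points limit how much the illustrative figures can carry. They do not supply an analysis that separates depth imaging from surface mapping with a default depth.

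**Conclusion.** The gap is real but moderate. Experiment 1 can describe absolute accuracy against the wire. As planned, it cannot show that depth imaging contributes to that accuracy.

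The size is illustrative only. A fixed 15 mm depth has a mean depth error of 3.3 mm on the simulated grid, assuming exact lateral position, a guess at the grid centre and equal weight on the three depths. Its pooled 3D error is about 3.3 to 5.1 mm for lateral error from zero up to half a pitch, and larger beyond that. This is of the same order as the plan's bound, but it does not meet that bound at every depth. The corresponding benchmark in patients is unknown, which is a reason to compute it from their data.

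A reader might go further and infer that no small LE could show any benefit of 3D imaging. That does not follow: an LE clearly below a comparator computed on the same motor units would show it. The plan provides no such comparator.

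**What to change.** Add the following to the Validation paragraph of Experiment 1.

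1. For each matched motor unit, compute a comparator LE to the same wire. Use the surface IZ for lateral position, or the surface position of the propagating activation zone when the wire is not in an IZ. Use mid-biceps depth from the ultrasound scan already taken, read from the muscle borders and not from the wire.
2. Take the paired difference, 3DIZI LE minus comparator LE. Average it within patient and report the mean over the eight patients with a 95% confidence interval.
3. Report depth error separately from lateral error, and the spread of wire depths across patients.
4. Claim added value of 3D imaging only if the interval favours 3DIZI. Otherwise report absolute accuracy only.

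A rule based only on which point estimate is smaller would not do, since two equivalent methods would pass it about half the time. Wire depths should not be preassigned to create spread, because that may conflict with the stated aim of placing the wire in an IZ.

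The cost is a little more analysis on data already collected, with no new patients, visits or procedures. The interval will be wide with eight patients, and the accuracy claim may turn out less favourable.

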The purpose of this Aim is to evaluate the feasibility of utilizing the 3DIZI technique to optimize BTX injections in patients with focal spasticity. Clinical and quantitative assessments of spastic biceps of stroke subjects between 3DIZI-guided and standard injections at baseline, 3 weeks, and 3 months post-injections will be compared. The clinical effect of BTX injection usually reaches to its peak at about 3 weeks, and lasts for 3 months. It is expected that outcomes (clinical and quantitative measures) will be better in the 3DIZI-guided injection group than in the standard injection group at 3 weeks and 3 months post-injection. Both groups are expected to have comparable baseline measures.

Patient selection: We plan to recruit 16 post-stroke subjects who are currently receiving BTX injections for their spastic biceps every 3 months at TIRR Outpatient Spasticity Management Clinic into two groups: the IZ-guided injection group and the standard injection group (Please see human subject protect section for characteristics of stroke patients).

BTX injections: Both groups of patients will be recruited prior to their routine BTX injection schedule. Baseline assessment (screening, clinical assessment, and quantitative assessment) will be performed 1 day prior to injection. Stroke patients with elbow flexors spasticity of modified Ashworth scale (MAS) of 2 or 3 will be recruited. The number of MAS (2s or 3s) will be matched between two groups. The type of BTX (we will choose botox because it is most commonly used in US) and amount of BTX (usually 100 units) and dilutions (usually double dilution) will be consistent between two groups. These parameters (type, dose, dilution) are standard of care at TIRR Spasticity Management Clinic. For standard injection procedures, target muscles will be visualized under ultrasound imaging which is operated by an experienced and dedicated technician. Position of needle tip within the target muscle is visualized prior to

[figure not shown]

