These measures will be made at baseline, 3 weeks and 3 months post-injection. Two-way ANOVA with factors of GROUP (x2) and TIME (x3) will be performed on reflex torque values. It is anticipated that MAS scores, reflex torque values are comparable at baseline, but will be significantly reduced at 3 weeks and 3 months for both groups. Reduction is expected to be significantly more in the IZ-guided injection group than in the standard group. We do anticipate great reduction in elbow flexor spasticity as quantified by reflex-torque measurement after the IZ-guided injection. However, MAS scores are not as reliable in general (Craven and Morris 2010), and could be influenced by other elbow flexors.

Pitfalls: If other elbow flexors are required to be injected but may not be consistent across subjects, it is unethical not to inject (treat) these muscles. Assessment of biceps spasticity may be influenced and thus MAS scores may not accurately reflect the spasticity reduction effect from biceps muscles alone. Efforts will be made to balance treatment plans between groups in the recruitment process.

Limitation: Eight patients and 16 patients (8 patients per group) are proposed for Exp 1 and Exp 2 respectively. We expect that 8 subjects in each group should be sufficient to detect difference should it exist, according a recent study (Lapatki et al. 2011). These estimated numbers fit in the scope of work of this 2-year exploratory project. A power analysis will be performed at the completion of this project to decide whether or how many more subjects will be needed for a future study. Full-time biostatisticians are available at both UH and TIRR (see Facilities and Other Resources section) for statistical analysis support.

The implementation of the 3DIZI technique currently proposed in the proposal is relatively complicated, because the main purpose of this project is to evaluate the performance of the proposed 3DIZI and examine the feasibility of its application to clinic. As the next step, we plan to simplify the implementation of the 3DIZI technique to make it appropriate for clinic use.

Specimens:

No specimens will be collected

5. Human Subjects

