- any condition that, in the judgment of a physician, would prevent the person from participating. Efforts will be made to match a variety of measures between two groups, such as age, gender, time from stroke, spasticity in other elbow flexors (e.g., brachioradialis), and injection sites. Given the volume of patients in TIRR Spasticity Management Clinic, we are confident that we can achieve this goal.

Potential subject populations and recruitment: Subjects will be recruited from TIRR outpatient clinic.

6. Data Collection and Analysis

A desktop computer will be used for data acquisition and processing. Data will be saved for off-line analysis using customized MatLab software and Statistica software.

Experiment 1: This is a validation study. Detailed information has been provided above.

Experiment 2: These measures will be made at baseline, 3 weeks and 3 months post-injection. Two-way ANOVA with factors of GROUP (x2) and TIME (x3) will be performed on reflex torque values. It is anticipated that MAS scores, reflex torque values are comparable at baseline, but will be significantly reduced at 3 weeks and 3 months for both groups. Reduction is expected to be significantly more in the IZ-guided injection group than in the standard group. We do anticipate great reduction in elbow flexor spasticity as quantified by reflex-torque measurement after the IZ-guided injection. However, MAS scores are not as reliable in general (Craven and Morris 2010), and could be influenced by other elbow flexors.

Demographic data will be analyzed descriptively. Personal information will be de-identified.

7. Potential Risks/Discomforts:

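### Groups are matched on entry MAS grade, but the reflex-torque model omits it; if MAS predicts torque, between-patient comparisons lose precision that one model term would recover

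*Combined protocol and SAP*

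**What the plan says.** In section 4, Experiment 2, under BTX injections, the protocol admits patients with MAS 2 or 3 and states: "The number of MAS (2s or 3s) will be matched between two groups". This balances counts; it does not form pairs. Section 5 adds softer intentions: "Efforts will be made to match a variety of measures between two groups, such as age, gender, time from stroke", along with spasticity in other elbow flexors and injection sites.

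The analysis appears in section 4 (Treatment outcome evaluation and comparison) and again in section 6: "Two-way ANOVA with factors of GROUP (x2) and TIME (x3) will be performed on reflex torque values". On timing: "These measures will be made at baseline, 3 weeks and 3 months post-injection". Baseline is therefore one of the three levels of TIME. The text names no MAS term and no patient or repeated-measures term, and does not say whether GROUP or GROUP x TIME decides the question.

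Two expectations are stated. The opening paragraph of Experiment 2 expects better outcomes in the guided group at 3 weeks and at 3 months, which reads as a group comparison at each visit. The analysis text says: "Reduction is expected to be significantly more in the IZ-guided injection group than in the standard group", which is a GROUP x TIME contrast.

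On size: "Eight patients and 16 patients (8 patients per group) are proposed for Exp 1 and Exp 2 respectively" and "We expect that 8 subjects in each group should be sufficient to detect difference should it exist". No alpha, power, effect size or SD is given.

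**The concern.** Balancing the number of MAS 2 and MAS 3 patients removes MAS from the difference between group means. A model without MAS still counts the spread between grades as error between patients. The estimated standard error then exceeds the true sampling error of the balanced comparison, so intervals are too wide and the test rejects too seldom. With 8 patients per group and no prospective power calculation, precision is scarce, and MAS grade is already recorded at entry.

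**Working it through.** **Inputs from the protocol.** 8 per group, three visits, MAS counts matched between groups.

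**Assumptions, because the protocol gives no figures.** Two-sided 5% level, no dropout, 4 patients of each grade per group, torque variance 1 at each visit, and a range for the share of variance explained by MAS.

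**The plan's own figure.** Without alpha, power, effect size or SD, 8 per group cannot be reproduced. For scale, an 8 v 8 t test (14 df) needs a difference of 1.51 SD for 80% power, and has 46% power at 1 SD.

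**Step 1: group comparison at one visit, 1 SD effect.** Let *s* be the MAS share of torque variance. With MAS balanced, the true variance of the mean difference is (1 − s)(1/8 + 1/8) = (1 − s)/4. Without MAS in the model, the expected pooled variance is [14(1 − s) + 16s]/14 = (1 − s) + 8s/7. On a root-mean-square basis the standard error is therefore too large by the factor √[1 + (8/7)·s/(1 − s)]. At s = 0.1 this is √1.127 = 1.06; at s = 0.4 it is √1.762 = 1.33. With MAS in the model, power follows from the noncentral t on 13 df with noncentrality 2/√(1 − s). The columns for MAS omitted come from simulation, except the zero row, which is exact.

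| MAS share | SE too large by | Type I error, MAS omitted | Power, MAS omitted | Power, MAS included |
|---|---|---|---|---|
| 0% | 0% | 5.0% | 46.1% | 45.7% |
| 10% | 6% | 3.9% | 45% | 50% |
| 20% | 14% | 2.8% | 45% | 54% |
| 30% | 22% | 1.9% | 43% | 60% |
| 40% | 33% | 1.1% | 42% | 67% |

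With MAS included, type I error stays at about 5% throughout. At zero share the cost is 46.1 − 45.7 = 0.4 points.

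**Step 2: repeated-measures ANOVA with a patient term, three visits.** Simulation with 40,000 trials per setting and an effect of 1.4 SD at both follow-up visits for the power columns. Here the MAS share is a share of between-patient variance, so 30% at a within-patient correlation of 0.5 is 15% of total variance. MAS shifts torque equally at all visits.

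| Correlation | MAS share | GROUP: type I error, MAS omitted | GROUP: power, omitted → included | GROUP x TIME, MAS omitted: type I error / power |
|---|---|---|---|---|
| 0.5 | 0% | 5.0% | 56.7% → 56.2% | 5.1% / 78.9% |
| 0.5 | 10% | 4.2% | 56.3% → 59.5% | 5.1% / 78.9% |
| 0.5 | 30% | 2.5% | 55.9% → 67.2% | 5.1% / 79.0% |
| 0.5 | 50% | 1.2% | 55.1% → 76.0% | 5.2% / 78.8% |
| 0.7 | 0% | 4.8% | 49.5% → 49.0% | 4.9% / 95.2% |
| 0.7 | 10% | 4.0% | 49.2% → 52.7% | 5.0% / 95.2% |
| 0.7 | 30% | 2.2% | 47.4% → 61.1% | 5.1% / 95.1% |
| 0.7 | 50% | 0.9% | 45.5% → 72.7% | 5.0% / 95.2% |

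The GROUP test shows the loss. GROUP x TIME does not: a stable MAS difference is absorbed by the patient term, and the GROUP x TIME F statistic is identical with and without a MAS main effect (28 error df both ways).

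**Step 3: reduction proportional to severity.** If every patient's torque falls by an assumed 50%, grade differences carry into the change scores. At correlation 0.7 and a MAS share of 30% to 40%, the change test that omits MAS has a type I error of 3.7% to 3.3%, and adjustment raises power from 65–66% to 70–72%. With a 30% reduction or a 10% share the gain is 0 to 2 points.

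**Step 4: the ANOVA read literally, 48 values treated as independent.** Over the same settings as step 2, the GROUP type I error is 7.4% to 20.5%; adding MAS alone moves it to 13.1% to 21.3%. GROUP x TIME is very conservative (0.0% to 0.5%), but it already is with no MAS effect (0.5% and 0.1%), so the missing patient term is the main cause.

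**The case against.** The strongest objection is that the plan's stated hypothesis is a larger reduction. That is GROUP x TIME, and with a patient term this test neither loses power nor becomes conservative when MAS shifts torque by a constant. This stands. A reader might infer that omitting MAS weakens the trial's central test; the documents do not support that, because nothing in them says that response differs by grade.

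A reader might also infer that the ANOVA as written is conservative throughout. Step 4 shows the opposite for GROUP when the patient term is missing, and there a MAS term alone makes matters worse. That stands too, and it governs how the fix must be made.

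Nor does the matching go to waste without the model term. No randomisation is described, so balance on severity limits confounding whatever model is fitted.

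Finally, the MAS share is unknown and may be small. Only two grades enter, the protocol itself calls MAS less than reliable and open to influence from other elbow flexors, and the end of the stretch is set relative to each patient's resting angle to offset baseline differences. In a 16-patient exploratory experiment, an error in the conservative direction is not grave. This limits the size of the point but does not remove it: the protocol also expects better outcomes at each follow-up visit, names no deciding contrast, and loses almost nothing by adjusting.

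**Conclusion.** The point holds in a limited form. If entry MAS grade predicts reflex torque, and once a patient term is in the model, comparisons between patients that omit MAS are conservative and lose power. At one visit with a 1 SD effect, adjustment gains about 5 points of power at a 10% share and about 25 at 40%. GROUP x TIME gains nothing under a constant MAS shift, and only about 1 to 7 points if the reduction scales with severity (50% reduction assumed). The figures rest on the assumed share, the 4/4 split, the within-patient correlation and the effect size, none of which the protocol gives. This is a cheap improvement and does not invalidate the planned comparison.

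**What to change.** In section 4 (Treatment outcome evaluation and comparison) and section 6 (Experiment 2), specify a repeated-measures or mixed model for reflex torque with:

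- a random patient term;
- GROUP, TIME and GROUP x TIME;
- entry MAS grade (2 v 3) as a between-patient factor;
- MAS x TIME, so that change contrasts are adjusted as well.

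Report the group differences with intervals at 3 weeks and 3 months from that model. The patient term must go in together with MAS, not after it.

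The cost is one between-patient degree of freedom (14 to 13) and two within-patient degrees of freedom for MAS x TIME (28 to 26). Power falls by under 1 point if MAS is uninformative, and MAS x TIME cost 0 to 1 point for GROUP x TIME under a constant MAS shift. No new data are needed. If the MAS counts end up unequal between groups, the same term also adjusts for the imbalance.
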